## 7.3 Recruitment

### 7.3.1 Patient sample identification

Potential participants will be identified by the clinical team. There exists an admissions list on the surgical assessment unit that has basic patient details (name, date of birth and hospital number) and presenting problem listed. This is regularly consulted by the clinical team as part of their clinical work. Eligible patients will be given basic information about the study by the clinical team at the point at which they are being discharged from their ambulatory stay on the surgical admissions unit. Patients interested in finding out more about the study will be given an information sheet and given the option of either leaving their telephone number for the study team to make contact or contacting the study team themselves using contact information given on the information sheet.

### **Staff recruitment**

**General surgical senior and junior doctors that work on the SAU will be given information about the study at relevant departmental meetings during the study recruitment period. It is likely that there will be a changeover of junior staff during this time so it may be necessary to repeat this briefing. At these meetings potential participants will have access to Information Sheets and will be able to complete an Expression of Interest form if they wish. Those that have completed an Expression of Interest form will be contacted in a manner of their choosing to answer questions, confirm interest and arrange a date for interview if they are happy to proceed.**

**Senior doctors will be given a choice of where they would like to perform the interview. A private room within the department will be available for booking but if consultants prefer to perform the interview from their private office this will be accommodated if possible. Junior doctors will be offered a booked private room within the surgical department or a private room booked near the SAU.**

**Ward staff will be given information about the study at departmental meetings and daily briefings as deemed appropriate by the Matron in charge of the ward. There will be the opportunity to take Information Sheets and complete Expression of Interest forms at this time and blank sheets and forms will be left on the ward as well. Staff completing Expression of Interest forms on the ward will be able to place them into an envelope within a drawer on the ward reception desk which the researcher will check regularly. Those that have completed an Expression of Interest form will be contacted in a manner of their choosing to answer questions, confirm interest and arrange a date for interview if they are happy to proceed.**

**A private room is available for booking in close proximity to the SAU that will be used for ward staff interviews. We have consulted the Matron in charge of SAU on the feasibility of facilitating staff interviews and it has been suggested that the best time would be before a shift starts or early on in their shift so we anticipate most interviews to take place between 0700-1100.**

**If any staff member wishes to take part but is unable to arrange time to do a face-to-face interview they will be offered the option of a telephone interview, the time of which will be scheduled in advance.**

### **7.3.2 Consent**

Potential participants who are interested in finding out more about the study will be given a **staff or patient** participant information sheet. This includes details of the study including the purpose of the study and method of data collection and details of how confidentiality will be ensured. They will be given the opportunity to ask for clarification and further questions at the first telephone contact meeting **(patients) or a follow-up discussion in their workplace or on email/telephone as preferred (staff).**

### **Patient consent**

Capacity will be assessed at the initial telephone contact and again prior to the interview if this is scheduled for a separate conversation. This will be done by exploring with potential participants their understanding of the purpose and nature of the research, the potential benefits (which will likely be to others rather than them as an individual) and risks. This will include how the data will be handled and confidentiality ensured. We will also ask participants if they have discussed their decision to participate with others and establish whether there has been any element of coercion to take part. Individuals deemed not competent to consent will not proceed to recorded interview.

A statement of consent will be taken at the start of the telephone interview and stored as a separate file for patient participants. This will include the following statements:

- that they have read and understood the information sheet
- participation is voluntary and there will be a period immediately after the interview for up to 2wks when they can change their mind about participating
- they understand that their care will not be affected by the decision to participate
- interviews will be recorded and then transcribed using an external transcription service. This will not include any sensitive information and they should take care not to mention sensitive information including their name and address in the interview.
- direct quotes may be taken from their interview to be published in the final research but will not contain any potentially identifiable information
- if any concerns about the participants ongoing health arise during the interview we are obliged to disclose these to their GP, however the GP will not be routinely contacted as part of the research process

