### 1 BACKGROUND

Abdominal pain is a common reason for people to attend hospital as an emergency. It makes up a considerable proportion of the patients being admitted under the care of general surgeons. Other common reasons for people attending include infections such as abscesses and problems following previous surgery.

A Surgical Assessment Unit (SAU) is an ambulatory area with a waiting room and assessment cubicles. It is staffed by a triage nurse or healthcare assistant and doctors from the surgical team. Patients can be assessed and have investigations including blood tests and radiology procedures including x-rays, ultrasound and CT. After assessment they are either admitted to the ward, discharged home or have their care continued in an ambulatory manner returning in the next few days for further or repeat assessment.

Previously patients were either discharged or admitted for observation, investigation and treatment such as intravenous antibiotics. Many of these patients could be managed safely in a "day case" manner. This pathway allows for re-attendance should it be required.

Emergency ambulatory care is well-established in medicine for conditions such as suspected deep vein thrombosis (DVT) and transient ischaemic attack (TIA) but has not yet been widely adopted in surgery.[1] There is uncertainty surrounding the best way of looking after these patients as the diagnosis is often uncertain and it can be difficult to judge which patients require admission.

Pilot studies have shown that up to 30% of emergency general surgical patients could be managed in this way.[2] These studies also report a high patient satisfaction score but do not inform us what works, why and for whom. These would be important considerations for organisations looking to expand their emergency general surgical ambulatory service.

This study aims to expand upon previous work in this area[3] by conducting semi-structured interviews with patients who have experienced emergency general surgical ambulatory care **and the staff who deliver this care.** We hope to identify themes that influence patient experience of emergency ambulatory care and whether this might vary depending on patient factors such as age, social support/responsibilities and attending condition.

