#### Interviews with patients

Participants will be recruited to the study by the clinical team by means of short verbal explanation and the provision of an information sheet. Potential participants will give their contact details to be passed to the study team or will make contact themselves at a later stage. They will then be contacted by the study team and given further information over the telephone. Those wishing to proceed will have arrangements made for a telephone interview. A recording of consent will be made prior to the start of the interview and will be stored as a separate audio file.

The interview schedule has been drawn up based on areas that have emerged from work in the past using patient diaries.[3] The PPI work done has included review of these questions for acceptability and ease of understanding and minor changes have been made to the wording of questions as a result. The prompts used are mainly to encourage explanations of why participants have answered the way they have.

The interviews will last 20-30mins and will be recorded using encrypted digital recording software. They will be conducted by the study co-ordinator. No potentially identifiable information will be recorded and participants will be advised not to divulge identifiable information prior to the interview. If this occurs inadvertently it will be deleted prior to transcription. These audio recordings will be given a unique identification number and then be transcribed into text documents using a paid professional transcription service within the UK. Once the transcription has been completed the recording will be deleted.

The transcribed data will be stored on a NHS server. It will be available for access to the study team by password protection and on request in an anonymised form by the University of Exeter sponsor if required for monitoring purposes. Once the study is complete it will be stored on the University of

Exeter Open Research repository for the period required for 5 years and securely deleted from the NHS server.

The transcribed data will be coded and then undergo thematic analysis using NVIVO software. Coding will be done by the principal investigator and a proportion of the data will be separately coded by the 2 senior members of the study team. Interim analysis will be conducted after each 5 patients and the interview schedule may undergo some change to explore in more detail areas of interest that emerge.

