## 8 ETHICAL AND REGULATORY CONSIDERATIONS

### Patient participants

There is no intervention in this study and it will not affect any care that patients receive in the future. The main potential risks to the participant are considered to be potential distress from discussing upsetting episodes of care they received and risk to their confidentiality by the use of direct quotes.

This study does not aim to explore particularly sensitive or personal aspects of a patient's care. The interview schedule has been reviewed by volunteers interested in helping with research design to check that the questions are deemed to be acceptable. Despite this, it is not possible to predict what each individual may find upsetting and sensitive to discuss. Participants who become distressed during the interview will be given the option to halt or terminate the discussion. Some participants may wish to share their experience although they find it upsetting, because they believe it is important for the purpose of the research and will be given the opportunity to do this if they wish but will not be directly prompted to do so.

Participants will be made aware during the consent process that direct quotations from their interview may be used but that they will be de-identified and great care will be taken that they do not include any potentially identifiable personal information. Participants who inadvertently identify themselves during the interview will be reminded by the interviewer to avoid revealing identifiable information. In this event this section of the recording will be erased and the participant prompted to try to express their statement again without the identifiable information.

The potential benefits of this study are to foster a greater understanding amongst healthcare professionals of how patients experience emergency ambulatory general surgical care which may help them deliver this care in a way that is deemed more acceptable to patients. It may also help those planning an expansion in this service to identify those most likely to engage well with this method of care delivery. It is possible that these benefits may be seen by patients undergoing similar care again in the future but it is likely that this will be a small number of participants.

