## 8.6 Data protection and confidentiality

All investigators will comply with the requirements of the Data Protection Act 1998 and subsequent revisions prompted by the General Data Protection Regulations (25th May 2018) with regards to the collection, storage, processing and disclosure of personal information and will uphold the Act's core principles and the University of Exeter's compliance requirements of the processing of data for research purposes as a task in the public interest.

All personal data collected during the course of the study will be either stored electronically on an encrypted, password-protected NHS computer hard drive or as paper files which will be stored in a locked drawer in a locked office with limited access. No NHS data will be transferred out of the NHS.

The participant interviews will be recording using a digital recording device by the principal investigator. Audio files of the participant consent procedure **(for those participants using telephone consent)** and the interviews will be downloaded from the recording device onto a secure hard drive and will be allocated a unique participant ID sequence with the ID key kept in a separate location as part of the pseudonymisation process. Prior to sending for transcription the interviews will be fully anonymised and the transcribed audio files will be securely destroyed once transcription is complete. This file will be stored in a secure password-protected encrypted file on an NHS server in a different location to the secure database containing the key.

A database linking the ID code to other information about the **patient** participants including sensitive data such as age, telephone number, presenting problem and distance from hospital will be stored separately in a secure password-protected encrypted file on an NHS server. **There will be a separate database for staff participants that will contain name, contact details and job title. These databases** will not be transferred elsewhere. **They** will be accessible only by the core members of the study team. **They** will be made available on request to the sponsor for the purposes of auditing or monitoring but will then have sensitive data such as telephone number removed. The sponsor will store the data on secure servers according to their protocols.

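### The patient consent statement restricts *sensitive* information where the methods restrict only *identifiable* information, so it is wider than intended and its assurance is inaccurate

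*Protocol*

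**What the plan says.** Protocol 7.3.2 (Patient consent) lists the statements recorded at the start of each patient telephone interview. After noting that the interview is recorded and transcribed by an outside service, it continues: "This will not include any sensitive information and they should take care not to mention sensitive information including their name and address in the interview". The next item, on published quotations, changes term and refers to potentially identifiable information.

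Elsewhere the interview restriction is put in terms of identifiability alone:
- Section 5 (Interviews with patients): "No potentially identifiable information will be recorded and participants will be advised not to divulge identifiable information prior to the interview". Anything identifying that slips through is deleted before transcription.
- Section 8 (Patient participants): "Participants who inadvertently identify themselves during the interview will be reminded by the interviewer to avoid revealing identifiable information". That part of the recording is erased, and the patient is asked to make the point again without the identifier.

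The word *sensitive* also has other uses. Section 8.6 describes the patient database as holding "sensitive data such as age, telephone number, presenting problem and distance from hospital". Section 8 uses the word in its everyday sense, for matters a person may find upsetting to talk about. It says that those who wish to share such an experience "will be given the opportunity to do this if they wish but will not be directly prompted to do so".

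Section 1 gives the substantive interest: themes in patient experience and "whether this might vary depending on patient factors such as age, social support/responsibilities and attending condition". Objective 4.1 asks why this form of care suits some people better than others.

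**The concern.** The data in this study are what patients say when asked to explain their experience. A caution given immediately before questioning should be no wider than confidentiality requires. The word *including* makes name and address examples of sensitive information, not its limit, so each patient is left to decide what else it covers.

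Two things are at stake. The first is the accuracy of consent: patients agree to a description of what is recorded and sent off site, and that description should be true. The second is the content of the interviews: a patient who takes the caution broadly may leave out details of the condition or of life at home, which are the explanations objective 4.1 needs.

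**Working it through.** No arithmetic drives this point; the protocol gives no figure to reproduce. The check compares how its sections use the two terms.

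1. **Width of the restriction.** Under 7.3.2 the restricted class is sensitive information, open-ended, with name and address as examples. Under sections 5 and 8 it is identifiable information. A presenting complaint described without a name is outside the second class, but it can fall inside the first, both on the section 8.6 label and on the everyday meaning used in section 8. The wording in 7.3.2 is therefore the wider.

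2. **Whether the assurance can be kept.** An interview about an emergency surgical attendance will naturally touch on the presenting problem. The removal steps in sections 5 and 8 act only on identifying content. Sections 6 and 8.6 add that interviews are fully anonymised before transcription, which again removes identity and not health content. Non-identifying health content therefore reaches the transcription service. If *this* in the 7.3.2 sentence means the transcription and not the interview, the result is the same, because the transcript reproduces the interview.

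3. **Consistency with section 8.** Section 8 lets patients share upsetting experiences if they choose. Read in its everyday sense, the 7.3.2 caution asks them not to mention what section 8 allows.

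4. **Overlap with the factors of interest.** Section 1 names three:
   - age: labelled sensitive in 8.6 and held in the linked database;
   - attending condition: labelled sensitive in 8.6 as presenting problem and held in the linked database;
   - social support/responsibilities: not labelled sensitive anywhere and not among the items 8.6 lists for the database.

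   Two of the three carry the label, and those two are available for analysis without being spoken. The database cannot supply the patient's own account of how the condition shaped the experience. For social support the interview is the only evident source.

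5. **Reach.** The statement is made in every patient interview: 20 of 20 planned, or 100%. That counts those who hear it, not those whose answers change.

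**The case against.** A reader might infer that patients are steered away from the very factors the study sets out to explore, and that its findings are biased as a result. The documents do not support that, for these reasons:

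- The only examples given to patients are identifiers, so the natural reading is that they should not identify themselves.
- Section 5 gives patients the narrower advice beforehand, and during the interview only identifying speech triggers a reminder. The patient is then asked to restate the point, which keeps the content.
- The same consent statement foresees concerns about ongoing health arising in the interview, and section 8.1 expects that mental well-being may come up. Health talk is anticipated, not barred.
- Nothing shows that patients hear the section 8.6 label. It describes a stored database, and later in the same paragraph the example of what is stripped for the sponsor is an identifier: "will then have sensitive data such as telephone number removed".
- Prompts seek explanations of why, and the schedule may be changed after each 5 patients.
- Section 7.3.2 lists statements in the third person and may not be the script. The information sheet and interview schedule are not shown.

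All of this stands, and it limits the point to wording. It does not remove the point. That the intent was identifiers is a reason to say so in the consent statement, and the inaccuracy about what is transcribed remains even if no patient holds anything back.

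**Conclusion.** The point holds as a minor wording defect in the consent statement. As written, 7.3.2 is open-ended and wider than sections 5 and 8 intend, and it assures patients of something the procedures do not deliver. It applies to all 20 planned patient interviews.

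Any loss of content is a possibility only. The protocol neither shows nor quantifies self-censoring. Age and presenting problem remain available from the linked database, and social support is nowhere called sensitive. The documents also give no basis for saying which patients would hold back most.

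The conclusion assumes that the statement spoken to patients follows the 7.3.2 wording and that interviews will mention the presenting problem.

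**What to change.** In 7.3.2 (Patient consent), replace *sensitive information* with *identifiable information (such as name and address)*, to match sections 5 and 8. Add that patients may talk about their condition and circumstances, and that this de-identified content will be transcribed externally. Align the information sheet if it uses the same wording.

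The cost is an amendment and slightly more content to check for identifiers before transcription. The change can help only interviews still to be held. The amendment history refers to early experience with patient participants, so some interviews may already be complete; the protocol does not say how many.

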### **Staff consent**

**Staff will be given the opportunity to express interest in the study and complete an expression of interest form. They will then be contacted in a manner of their choosing for a follow-up discussion within 2 weeks when any questions about the study can be answered and interest confirmed. At this time arrangements will be made to complete an interview. This may require follow-up correspondence to secure an appropriate time and room booking. This period of time between initial information and interview will give staff time to consider the decision to take part.**

**Staff conducting a face-to-face interview will read and sign a copy of the staff consent form prior to the start of the interview. A copy of the consent form will be given to staff participants for their records.**

## 8 ETHICAL AND REGULATORY CONSIDERATIONS

### Patient participants

There is no intervention in this study and it will not affect any care that patients receive in the future. The main potential risks to the participant are considered to be potential distress from discussing upsetting episodes of care they received and risk to their confidentiality by the use of direct quotes.

This study does not aim to explore particularly sensitive or personal aspects of a patient's care. The interview schedule has been reviewed by volunteers interested in helping with research design to check that the questions are deemed to be acceptable. Despite this, it is not possible to predict what each individual may find upsetting and sensitive to discuss. Participants who become distressed during the interview will be given the option to halt or terminate the discussion. Some participants may wish to share their experience although they find it upsetting, because they believe it is important for the purpose of the research and will be given the opportunity to do this if they wish but will not be directly prompted to do so.

Participants will be made aware during the consent process that direct quotations from their interview may be used but that they will be de-identified and great care will be taken that they do not include any potentially identifiable personal information. Participants who inadvertently identify themselves during the interview will be reminded by the interviewer to avoid revealing identifiable information. In this event this section of the recording will be erased and the participant prompted to try to express their statement again without the identifiable information.

The potential benefits of this study are to foster a greater understanding amongst healthcare professionals of how patients experience emergency ambulatory general surgical care which may help them deliver this care in a way that is deemed more acceptable to patients. It may also help those planning an expansion in this service to identify those most likely to engage well with this method of care delivery. It is possible that these benefits may be seen by patients undergoing similar care again in the future but it is likely that this will be a small number of participants.

Telephone interview has been selected as the method of data collection for **patient participants** in this study as it is thought to be a method which minimises inconvenience and intrusion to the participants. The timing of the interviews is planned to be 1-2 weeks after the ambulatory attendance episode to give potential participants time to reflect on their experience and time to consider whether they would be willing to take part in the study and feel free from any sense of obligation to the staff who may have initially approached them regarding the study.

